dL	deciliter
DLT	Dose–Limiting Toxicity
ECG	Electrocardiogram
FDA	Food and Drug Administration
FEF ₂₅₋₇₅	Forced Expiratory Flow between 25 and 75% of the FVC
FEV ₁	Forced Expiratory Volume in 1 second
FVC	Forced Vital Capacity

This document is confidential.

Statistical Analysis Plan for Interventional Studies

Sponsor: Armata Pharmaceuticals, Inc.; Protocol No.: AP-PA02-101

Abbreviation	Description
GCP	Good Clinical Practice
GLI	Global Lung Function Initiative
ICH	International Conference on Harmonization
INR	International Normalized Ratio
kg	kilogram
L	liter
LABA	long-acting inhaled β -agonist
LLQ	lower limit of quantification
LPS	lipopolysaccharide
MAD	Multiple Ascending Dose
Max	Maximum
μ g	microgram
μ L	microliter
MedDRA	Medical Dictionary for Regulatory Activities
mEq	milliequivalent
mg	milligram
mL	milliliter
mmHg	millimeters of mercury
mmol	millimole
Min	Minimum
MOI	multiplicity of infection
N/A	Not Applicable
NA	Not Applicable
OR	Observational Research
PASS	Post Authorization Safety Study
PAES	Post Authorization Efficacy Study
Pa, P. aeruginosa	Pseudomonas aeruginosa
PFU	plaque-forming unit
PT	prothrombin time, preferred term
PTT	partial thromboplastin time
qs	quantity sufficient

This document is confidential.

Statistical Analysis Plan for Interventional Studies

Sponsor: Armata Pharmaceuticals, Inc.; Protocol No.: AP-PA02-101

Abbreviation	Description
QTc	corrected QT interval
QTcB	corrected QT interval using Bazett's formula
RR	respiratory rate
SABA	short-acting inhaled β -agonist
SAD	Single Ascending Dose
SAE	Serious Adverse Event
SAP	Statistical Analysis Plan
SMC	Safety Monitoring Committee
SD	Standard Deviation
SE	Standard Error
SI	Standard International System of Units
SOC	System Organ Class
SOP	Standard Operating Procedure
SUSAR	Suspected Unexpected Serious Adverse Reaction
ULN	upper limit of normal
TEAE	Treatment Emergent Adverse Event
TFL	Table, Figure and Figure
WHO	World Health Organization

This document is confidential.

2. Purpose

The purpose of this statistical analysis plan (SAP) is to ensure that the data listings, summary tables and figures which will be produced, and the statistical methodologies that will be used, are complete and appropriate to allow valid conclusions regarding the study objectives.

This SAP is created based on Protocol Number AP-PA02-101 version 6.0 dated 13 August 2021. The purpose of this SAP is to outline the planned analyses by Syneos Health (SYNH) to support the completion of the Clinical Study Report (CSR). This SAP describes in detail the statistical methodology and the statistical analyses to be conducted for the above mentioned protocol. The planned analyses identified in this SAP is following the Statistical Principles for Clinical Trials such as International Council for Harmonisation (ICH) guidelines, E4, and E9.

2.1. Responsibilities

Syneos Health will perform the statistical analyses and are responsible for the production and quality control of all SDTMs and ADaM datasets, and tables, figures and listings.

2.2. Timings of Analyses

The primary analysis of safety and efficacy is planned after all subjects complete the final study visit or terminate early from the study. Unless otherwise specified, the analysis includes all data collected in the database through the time of the database lock. Analyses related to phage counts may be conducted by another entity, and as such are listed in this SAP for completeness, although no datasets and outputs are planned to be programmed by Syneos at this time,

No formal interim analyses for efficacy or futility are planned.

This document is confidential.

3. Study Objectives

3.1. Primary Objective

Part 1: SAD Evaluation: Evaluate the safety and tolerability of a single dose of AP-PA02 administered via inhalation.

Part 2: Multiple Ascending Dose (MAD) Evaluation: Evaluate the safety and tolerability of multiple doses of AP-PA02 administered via inhalation.

3.2. Secondary Objective(s)

Part 2: MAD Evaluation: To explore *P. aeruginosa* recovery in sputum following multiple doses of AP-PA02 administered via inhalation.

3.3. Exploratory Objectives

Part 1: SAD Evaluation: Examining phage distribution and clearance, evidence of clinical efficacy, and the impact of phage therapy on the bacterial target after a single dose of AP-PA02 administered via inhalation.

Part 2: MAD Evaluation: Examining phage distribution and clearance, evidence of clinical efficacy, and the impact of phage therapy on the bacterial target.

3.4. Brief Description

This is a Phase 1b/2a, double-blind, randomized, placebo-controlled, single and multiple ascending dose study to evaluate the safety, tolerability and phage titer profile of AP-PA02 administered by inhalation.

3.4.1. Part 1: SAD Evaluation

[figure not shown]
Part 1 will evaluate single ascending doses of AP-PA02 administered by inhalation in medically stable cystic fibrosis patients with pulmonary *P. aeruginosa* infection at time of Screening. A total of 8 subjects, 4 subjects in each of 2 sequential ascending dose cohorts, will be randomized to receive either AP-PA02 or placebo administered via inhalation at the clinical site. Each cohort of 4 subjects will be randomized with 3 subjects to receive active treatment and 1 subject to receive placebo.

Once enrolled, each subject will receive a single dose of AP-PA02 (or placebo) on Day 1. Subjects will be followed for safety and phage titer profiles for up to 4 weeks post-dose. The first two subjects of the same dose cohort will not be permitted to dose on the same day to allow for adequate safety monitoring between subjects.

The Safety Monitoring Committee (SMC) will review all available safety data through Visit 4 for each SAD cohort (including any additional safety data from the prior SAD cohorts collected to date), before continuing to the next SAD dosing cohort.

This document is confidential.

Figure 3.1 Enrollment by Cohort Schematic

3.4.2. Part 2: MAD Evaluation

The MAD portion of the study will also be double-blinded, randomized, placebo-controlled, to evaluate the safety and efficacy of two dose levels of AP-PA02. The first MAD cohort (Cohort 3) will enroll 4 subjects, where 3 subjects will be randomized to active treatment and 1 subject randomized to receive placebo. The second MAD cohort (Cohort 4) will enroll 20 subjects, where 15 subjects will be randomized to receive active treatment, and 5 subjects will be randomized to receive placebo. The total number of placebo patients will be 6 subjects across the two dose cohorts.

Each cohort will be randomized at a 3:1 ratio.

Initiation of enrollment into the MAD portion of the study will be dependent on the positive recommendation and concurrence of the Sponsor following the SMC review following Cohort 2.

Cohort 3 of the MAD portion will be enrolled first, followed by Cohort 4. Once enrolled, each subject will receive one fractionated dose of AP-PA02 or placebo (one dose distributed over two administrations by inhalation in the same day), at least 6 hours apart, for five or ten consecutive days in the clinic for Cohorts 3 or 4, respectively. For Cohort 3, subjects will return to the clinic approximately 24 hours post-last dose for safety evaluations and phage titer sampling, for Visits 6 through 8, and End of Study Visit. For Cohort 4, subjects will return to the clinic approximately 24 hours post-last dose for safety evaluations and phage titer sampling, and on Visits 11 through 13, and End of Study Visit. A follow-up visit for safety and ADA titer will be performed at the End of Study Visit. The first two randomized subjects of each dose cohort will not be permitted to initiate dosing (Day 1) on the same day, to allow for adequate safety review.

This document is confidential.

The SMC will review all available safety data through Visit 7 for Cohort 3 (including any additional safety data from the SAD cohorts collected to date), before continuing to the next MAD dosing cohort.

3.5. Subject Selection

Subjects with cystic fibrosis and chronic pulmonary *Pa* infection who meet all inclusion and exclusion criteria will be eligible for participation in this study. The full list of inclusion and exclusion criteria is provided in Section 6.1.1 and 6.1.2 of the protocol.

3.6. Determination of Sample Size

The sample size is not based on power calculations; it is chosen based on clinical experience and considered to be adequate to fulfill the objectives of the study.

Eight subjects were planned to be enrolled in the SAD portion of the study, with 4 subjects per cohort (3 AP-PA02 and 1 placebo).

Approximately 24 subjects will be enrolled in the MAD portion of the study, with 4 subjects in Cohort 3 (3 AP-PA02 and 1 placebo) and 20 subjects in Cohort 4 (15 AP-PA02 and 5 placebo). The exact number of subjects enrolled is dependent on whether any dose level is to be expanded due to the occurrence of dose-limiting toxicities (DLT).

3.7. Treatment Assignment & Blinding

This study has a single-dose phase and a multiple-dose phase and will include 4 separate cohorts based on [Sections 3.4.1](#) and [3.4.2](#) (Figure 3.1).

The single-dose phase (Cohorts 1 and 2) will enroll subjects with medically stable cystic fibrosis with pulmonary *P. aeruginosa* infection at time of Screening prior to conducting a multiple-dose phase (Cohorts 3 and 4) in additional subjects.

The treatment allocation ratio for each SAD and MAD cohort will be 3:1, AP-PA02 to placebo. Due to the fact that there are four subjects per SAD cohort, at least one of the first two subjects enrolled in each cohort will be randomized to receive AP-PA02.

The first two subjects enrolled into the same SAD cohort will not be permitted to dose on the same day, to allow for adequate review of safety by the study Medical Monitor and/or Sponsor designee following dosing, as reported by the Investigator. If there are no significant findings for the first two subjects following their dosing, as reported by the Investigator(s), the remaining subjects of the cohort are permitted to undergo study drug dosing.

Within each MAD dosing cohort, subjects will be randomized 3:1, AP-PA02 to placebo. At least one of the first two subjects enrolled in each cohort will be randomized to receive AP-PA02. The first two subjects enrolled into the same MAD cohort will not be permitted to initiate study drug dosing (Day 1) on the same day, to allow for review of adequate safety by the study Medical Monitor and/or Sponsor designee following dosing as reported by the Investigator. If there are no significant safety findings for the first two subjects following their respective Dosing Day 1 as reported by the Investigator, the remaining subjects are permitted to initiate study drug dosing (Day 1).

Study drug will be administered in a double-blind fashion. Study drug and placebo are both clear, colorless, and odorless aqueous solutions. Subjects, Investigators and study staff will be blinded to treatment assignment.

Rave RTSM will be used to assign subjects to treatment using a list of randomization codes generated by a randomizing statistician. No stratification factors will be used.

This document is confidential.

The subjects and all site personnel, including the investigator, the site monitor, and the study team, will be blinded with the exception of the following:

- RSG Project Lead
- Clinical Supply Manager
- Unblinded CRA
- Unblinded Lead CRA
- Unblinded Site Pharmacist
- Depot Users

Unblinding will occur after database lock and during review by the Safety Monitoring Committee (SMC).

3.8. Administration of Study Medication

Study drug doses will only be administered by a healthcare professional in an in-clinic setting. At-home dose administration will be allowed under supervision of a healthcare professional. Subjects will receive study drug by inhalation via the study-designated nebulizer.

Full details are available in the Investigational Medicinal Product and Nebulizer Sections 3.1 and 3.2 of the protocol.

3.9. Study Procedures

The study procedures to be performed as summarized in the Schedule of Assessments, is provided in the protocol Appendix 1, Schedule of Assessments.

This document is confidential.

4. Endpoints

4.1. Primary Endpoint

4.1.1. Part 1: SAD Evaluation

The primary endpoints of Part 1 of the trial are the incidence and severity of treatment-emergent adverse events (TEAEs), occurring from Day 1 pre-dose through the End of Study (EOS) Visit

4.1.2. Part 2: MAD Evaluation

The primary endpoints of Part 2 of the trial are the incidence and severity of TEAEs, occurring from Day 1 pre-first dose through the EOS Visit.

4.2. Secondary Endpoints

4.2.1. Part 2: MAD Evaluation

The secondary endpoint for the MAD portion of the trial is a change in *P. aeruginosa* colony-forming units (CFU) per gram of sputum from the Baseline visit through approximately 14 days after the last dose of study drug.

4.3. Exploratory Endpoints

4.3.1. Part 1: SAD Evaluation

- Phage titer profile in sputum, blood, and urine over time after a single dose of AP-PA02 administered via inhalation
- Change in FEV₁ (% predicted and absolute volume) from Day 1 pre-dose through EOS Visit
- Change in Cystic Fibrosis Questionnaire-Revised (CFQ-R) from Day 1 pre-dose through the EOS Visit
- Changes in the Cystic Fibrosis Respiratory Symptom Diary (CFRSD) and Chronic Respiratory Infection Symptom Score (CRISS) from Day 1 pre-dose through the EOS Visit
- Change in *P. aeruginosa* CFU per gram of sputum from Baseline through Visit 5
- Change in *P. aeruginosa* isolates' sensitivity to AP-PA02 and/or its individual components from Screening through the Visit 5
- Change in *P. aeruginosa* isolates' sensitivity to antipseudomonal antibiotics from Baseline through Visit 5

4.3.2. Part 2: MAD Evaluation

- Phage titer profile in sputum, blood, and urine over time after multiple doses of AP-PA02 administered via inhalation
- Change in FEV₁ (% predicted and absolute volume) from Day 1 pre-dose through the EOS Visit
- Change in CFQ-R from Day 1 pre-dose through the EOS Visit
- Changes in the CFRSD and CRISS from Day 1 pre-dose through the EOS Visit
- Change in *P. aeruginosa* isolates' sensitivity to AP-PA02 and/or its individual components from Screening through approximately 14 days after the last dose of study drug
- Change in *P. aeruginosa* isolates' sensitivity to antipseudomonal antibiotics from Baseline through approximately 14 days after the last dose of study drug.

This document is confidential.

5. Analysis Sets

5.1. Safety/Efficacy Population

The safety population will include all subjects who receive any AP-PA02 or placebo. Subjects will be analyzed according to treatment received. This population will be used for all analyses of safety endpoints and for the presentation of subjects in all subject listings including subject disposition.

5.2. Major Protocol Deviations

In the event of a major protocol deviation, the Investigator and Sponsor's Medical Monitor and/or designee will determine whether the subject should continue to participate in the study. The Investigator should notify the IRB/IEC of deviations from the protocol or SAEs occurring at the site.

This document is confidential.

6. General Aspects for Statistical Analysis

6.1. General Methods

All analyses and summaries will be produced using Statistical Analysis System (SAS®) version 9.4 or higher. All SAS programs used to generate analytical results will be developed and validated according to SYNH programming standards and SAS validation procedures. Summaries will be presented by cohort/dose group and overall unless otherwise specified. Each active treatment group will be labeled in the outputs by its Phage Cocktail and estimated total protein per total plaque-forming units (PFU) for each dose for the SAD cohorts and the total dose per treatment course for the MAD cohorts. Additionally, pooled placebo will be presented.

The naming convention for the listings include:

- Cohort 1 Single Ascending Dose (SAD): 3-Phage Cocktail, AP-PA02 (1E10 PFU single dose)
- Cohort 1 Single Ascending Dose (SAD): 3-Phage Cocktail, Placebo
- Cohort 2 Single Ascending Dose (SAD): 3-Phage Cocktail, AP-PA02 (3E10 PFU single dose)
- Cohort 2 Single Ascending Dose (SAD): 3-Phage Cocktail, Placebo
- Am5 SAD: Single Ascending Dose (SAD): 3-Phage Cocktail, AP-PA02 (9E10 PFU single dose)
- Am5 SAD: Single Ascending Dose (SAD): 3-Phage Cocktail, Placebo
- Am5 MAD: Multiple Ascending Dose (MAD): 3-Phage Cocktail, AP-PA02 (1E10 PFU/dose x 3 doses/day x 3 days)
- Am5 MAD: Multiple Ascending Dose (MAD): 3-Phage Cocktail, Placebo
- Cohort 3 Multiple Ascending Dose (MAD): 5-Phage Cocktail, AP-PA02 (5.75E10 PFU/dose x 2 doses/day x 5 days)
- Cohort 3 Multiple Ascending Dose (MAD): 5-Phage Cocktail, Placebo
- Cohort 4 Multiple Ascending Dose (MAD): 5-Phage Cocktail, AP-PA02 (1.5E11 PFU/dose x 2 doses/day x 10 days)
- Cohort 4 Multiple Ascending Dose (MAD): 5-Phage Cocktail, Placebo
- "Screen Failures" if applicable

The naming convention for the tables and figures include:

- Cohort 1: 3-Phage (1E10 PFU SD)
- Cohort 2: 3-Phage (3E10 PFU SD)
- Cohort 3: 5-Phage (5.75E10 PFU/dose x 2 doses/day x 5 days)
- Cohort 4: 5-Phage (1.5E11 PFU/dose x 2 doses/day x 10 days)
- Pooled Placebo

Pooled Placebo group in the tables and figures will include Protocol Amendment 5 subjects.

Results for subjects assigned to either of the following dose groups will be included in the listings only:

- Am5 SAD: Single Ascending Dose (SAD): 3-Phage Cocktail, AP-PA02 (9E10 PFU single dose)
- Am5 MAD: Multiple Ascending Dose (MAD): 3-Phage Cocktail, AP-PA02 (1E10 PFU/dose x 3 doses/day x 3 days)

Unless otherwise noted, continuous variables will be summarized using the number of non-missing observations (n), arithmetic mean (Mean), standard deviation (SD), median, minimum, and maximum values as summary statistics. The minimum and maximum will be displayed to the precision with which the data were collected. The mean, median and quartiles will be displayed to one additional decimal place and the SD will be displayed to two additional decimal places, where applicable.

Descriptive statistics for categorical/qualitative data will include frequency counts and percentages. The total number of subjects with a non-missing value for the given variable will be used as the denominator for percent calculations, unless stated otherwise. All percentages will be presented with one decimal,

This document is confidential.

unless otherwise specified. Percentages equal to 100 will be presented as 100, and percentages will not be presented for zero frequencies.

All relevant subject data will be included in listings. All subjects entered into the database will be included in subject data listings.

A decision to close the study early was made by the Sponsor, and not all planned analysis outputs may be required.

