8.2.3. Change in *P. aeruginosa* isolates' sensitivity to antipseudomonal antibiotics

Analysis of this exploratory endpoint will not be performed by Syneos Health.

8.2.4. Change in Cystic Fibrosis Questionnaire-Revised (CFQ-R) from Day 1 pre-dose through end of study

Cystic Fibrosis Questionnaire-Revised (CFQ-R) subject health-related quality of life questionnaire assesses 12 domains: physical functioning, role functioning, vitality, emotional functioning, social functioning, body image, eating problems, treatment burden, health perceptions, weight, respiratory symptoms, and digestive symptoms.

Each domain is composed of a variable number of self-report questions with distinct 4-point Likert scales (e.g., always/often/ sometime/never), with a total of 50 questions. CFQ-R general scoring instructions are provided in [Appendix 15.1](#). Each of the CFQ-R domains scores range from 0 to 100, with higher scores indicating a higher patient-reported quality of life with regard to the domain being evaluated. Domain scores are derived only when >50% of domain items are not missing.

The CFQ-R domain scaled score and absolute change from baseline will be summarized by visit using summary statistics for continuous variables by cohort and overall for each study part.

8.2.5. Changes in the Cystic Fibrosis Respiratory Symptom Diary (CFRSD) and Chronic Respiratory Infection Symptom Score (CRISS) from Day 1 pre-dose through the end of the study

The Cystic Fibrosis Respiratory Symptom Diary – Chronic Respiratory Infection Symptom Score (CFRSD-CRISS) is a subject-reported outcome that measures respiratory symptoms in cystic fibrosis using standard qualitative methods, includes 16 questions (8 symptom items, 4 emotional impact items, and 4 activity impact items) and takes less than 5 minutes to complete.

This document is confidential.

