- TEAEs leading to permanent withdrawal of study drug, overall and by SOC and PT
- Study Drug-related TEAEs leading to permanent withdrawal of study drug, overall and by SOC and PT
- TEAEs of Interest by SOC and PT
- DLTs by SOC and PT
- DLTs by severity, SOC and PT
- TEAEs which resulted in death, overall and by SOC and PT

If a subject has more than one event within a given SOC or PT at different severities, the maximum severity will be tabulated. For example, if a subject experiences two events with the same preferred term,

This document is confidential.

but one was at moderate and the other at severe severity, the severe TEAE will be included in the tabulation. Severity is classified into five categories: mild, moderate, severe, life-threatening and death.

An AE will be considered drug-related if the relationship attribution designation is missing. AEs with a missing onset date, but with stop date either missing or on or after the date of first dose of study drug will be included as treatment emergent. All AEs will be listed in subject listing, and summarized by numbers and percent of subjects by dose for each portion of the study separately. If a subject reports the occurrence of a particular event more than once, the most severe of those events will be included in the summary tables of TEAEs, and the most severe of the treatment-related events will be included in the summary tables of treatment-related events.

If the severity or relationship to study drug, study device or study procedure, is missing for an AE, the event will be assumed to have severity level of 'severe' or the maximum relationship (i.e. definitely), respectively. If the seriousness status is missing for an AE, the event will be assumed to be serious.

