9.3. Laboratory Evaluations

Laboratory measurements (hematology, chemistry, urinalysis, and coagulation) obtained at baseline and each study visit will be summarized by dose group in the following ways:

- Descriptive statistics of actual results and changes from baseline (number of subjects, mean, standard deviation, median, minimum, and maximum) for the continuous data and frequencies and percentages for the categorical data, for each assessment visit

This document is confidential.

- Potentially clinically significant lab abnormalities for hematology, chemistry and coagulation will be summarized by study part, dose group and assessment visit.
- By-subject line plots will be presented by lab parameter, study part and dose group, to allow for significant out of range values to be further identified

By-subject safety laboratory listings will be generated incorporating information and assessment results obtained from the designated laboratory which provided normal range and reported out of range results. All laboratory results in SI units will be presented in data listings. Tests will be listed in alphabetical order within their respective panels (hematology, serum chemistry, urinalysis, and coagulation).

Potentially clinically significant hematology and chemistry laboratory results will be summarized using severity grades according to NCI CTCAE (version 5.0 or higher) where applicable. The worst post-baseline severity grade will be summarized and is defined as the most severe toxicity grade of the specific parameter assessed during the study at a scheduled or unscheduled visit. If a severity grade scale is missing for a laboratory parameter, the normal ranges of the clinical laboratory will be used.

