9.4. Vital Signs

Vital sign measurements will consist of heart rate, respiratory rate, pulse, blood pressure (systolic and diastolic), temperature and oximetry. Descriptive summaries (number of subjects, mean, standard deviation, median, minimum, and maximum) of actual values and changes from pre-dose will be presented for each visit and time point, by study part and dose group. These summaries will be presented for the safety population and by dose cohort. Vital signs will be performed at prespecified time points per the Schedule of Assessments in Appendix 1 of the Protocol.

This document is confidential.

Temperature will be summarized in Celsius (C) units. Fahrenheit (F) will be converted to Celsius using the following conversion:

$$(\text{Temperature (F)} - 32) * 5/9 = \text{Temperature (C)}$$

Potentially clinically significant (PCS) vital sign abnormalities will be categorized based on Table 10.4.1, and summarized by study part, dose group and assessment visit.

Table 10.4.1: Potentially Clinically Significant Values for Vital Signs

Vital Sign Parameter	Units	Criteria for PCS Values (Observed values)		Criteria for PCS values (Change from Baseline values)	
		High	Low	Increase	Decrease
Heart rate (sitting)	Beats/min	>120	<40	NA	NA
Systolic Blood Pressure (sitting)	mmHg	>180	<90	≥30	≥30
Diastolic Blood pressure (sitting)	mmHg	>110	<50	≥20	≥20
Oxygen Saturation (sitting)	%	NA	<92	≥5	≥5

Vital signs data will be listed chronologically by subject and visit for each vital sign parameter.

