9.7. Spirometry

Spirometry assessments FEV₁, FVC, and FEF₂₅₋₇₅ will be collected to evaluate for provoked bronchospasm. Actual liter values will be recorded. Details regarding spirometry procedures and standards will be included in the Study Manual.

Observed values and mean changes from baseline will be presented for each spirometry parameter using descriptive statistics (i.e. n, mean, standard deviation, median, minimum, and maximum) by dose group and visit, using the Safety population. If multiple measurements are to be performed at each time point, the highest value will be used for analysis.

A by-subject listing will be provided, including each spirometry parameter, and will be sorted by subject and visit.

A by-subject line plot will be presented by spirometry parameter, study part and dose group. Each dose group will be on a new plot, with all subjects of the same dose group on the same plot. Any unscheduled results will also be part of this plot.

The number and percentage of participants with PCS values will be summarized by visit/timepoint and for any time post-baseline. Potentially clinically significant values will be identified for FEV₁ (forced expiratory volume) as outlined below.

Table 10.7: Potentially Clinically Significant Values for Forced Expiratory Volume Decrease

Parameter	Units	Criteria for PCS Values (Observed values)	
		High	Low
Forced Expiratory Volume	%	NA	70 – 99 60 – <70 50 – <60 <50

This document is confidential.

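### The single pooled placebo group in SAP 6.1 is not limited to a study part, so laboratory and spirometry tables without a part split can mix times relative to dosing at one visit number

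*SAP*

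**What the plan says.** SAP 6.1 sets five groups for tables and figures: Cohorts 1 to 4 and one pooled placebo group. It adds that "Pooled Placebo group in the tables and figures will include Protocol Amendment 5 subjects". The listing names in the same section show that Amendment 5 had both a SAD and a MAD placebo group. The default layout is "Summaries will be presented by cohort/dose group and overall unless otherwise specified", which does not mention study part. SAP 6.4 derives no visit windows and uses nominal visits for by-visit tables.

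Several later sections do name the part:

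- CFQ-R (8.2.4): "summary statistics for continuous variables by cohort and overall for each study part"
- Adverse events (9.2): "summarized by numbers and percent of subjects by dose for each portion of the study separately"
- Vital signs (9.4): "will be presented for each visit and time point, by study part and dose group"
- Laboratory PCS abnormalities (9.3): "lab abnormalities for hematology, chemistry and coagulation will be summarized by study part, dose group and assessment visit"
- Laboratory line plots (9.3) and spirometry line plots (9.7)

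Others do not:

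- Laboratory descriptive statistics (9.3): "obtained at baseline and each study visit will be summarized by dose group in the following ways"
- Spirometry descriptive statistics (9.7): "by dose group and visit, using the Safety population"
- Spirometry PCS counts (9.7): by visit or timepoint only
- FEV1 change, absolute and % predicted (9.7.1): by visit only

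**The concern.** Where a section names no part, a programmer falls back on the 6.1 default and builds one placebo column from every placebo subject in the trial. That is harmless only if a visit number means the same thing in every cohort. It does not, because the SAD cohorts receive one dose, Cohort 3 is dosed for five days and Cohort 4 for ten.

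At stake is whether the placebo row can serve as a comparator. If it mixes end-of-study, post-dosing and dosing-period values, it cannot be read against an active cohort's row at the same visit number. This matters most for spirometry, which 9.7 says is collected to look for provoked bronchospasm, and for FEV1 change, an exploratory endpoint in both parts (4.3). With so few placebo subjects, one or two misaligned values can move a mean.

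**Working it through.** **1. Planned placebo numbers.** Allocation is 3:1 (SAP 3.7), so placebo = cohort size / 4.

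- MAD: 4/4 + 20/4 = 1 + 5 = 6, which reproduces the total in 3.4.2.
- SAD: 4/4 + 4/4 = 2, in line with 3.4.1.
- All four cohorts: 2 + 6 = 8, plus an unstated number from Amendment 5.

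If Amendment 5 contributed 0 to 2 placebo subjects in each part (an assumption), the pooled N is 8 to 12. The SAD share is then between 2/10 = 20% and 4/10 = 40%.

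**2. What the visit numbers mean.** Visit 1 is Day 1 in all cohorts (6.2.1).

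| Group | Dosing | Post-dosing visits | EOS |
|---|---|---|---|
| SAD | single dose, Day 1 | follow-up to 4 weeks (3.4.1) | Visit 6 (8.2.5) |
| Cohort 3 | 5 days | from Visit 6 (3.4.2, 8.2.5) | Visit 9 |
| Cohort 4 | 10 days | from Visit 11 (3.4.2, 8.2.5) | Visit 14 |

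On the natural reading of 3.4.2, Cohort 3 Visit 6 is about 24 hours after the last dose. That Cohort 4 Visits 1 to 10 are dosing visits is inferred: Visit 1 is Day 1, there are ten consecutive dosing days, and post-dosing visits are numbered from 11.

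**3. Illustrative make-up of a Visit 6 placebo row.** This uses planned n, leaves out Amendment 5, and assumes the assessment is done at Visit 6 in each cohort named.

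| Cohorts in the row | End of study | Post-dosing | Dosing (inferred) |
|---|---|---|---|
| SAD + Cohort 3 | 2/3 = 67% | 1/3 = 33% | – |
| All four cohorts | 2/8 = 25% | 1/8 = 12.5% | 5/8 = 62.5% |
| MAD only | – | 1/6 = 17% | 5/6 = 83% |

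The first row does not need the inference about Cohort 4. The third shows that a part split alone does not align the MAD data.

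**4. Which MAD visit numbers mix phases.** Cohort 3 post-dosing visits are {6, 7, 8, 9} and inferred Cohort 4 dosing visits are {1, ..., 10}. The overlap is {6, 7, 8, 9}, or {6, 7, 8} if EOS is tabulated under its own label. In that case SAD also leaves the Visit 6 row.

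**5. The MAD range in 8.2.5.** For the symptom diary score, 8.2.5 summarizes MAD visits from 2 to 8/EOS. The next paragraph lists Cohort 3 visits up to 9 and Cohort 4 visits up to 14. Read literally, the range leaves out Cohort 4 Visits 11 to 13, for which the same section defines averaged diary scores.

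**The case against.** The best defence is that the intent is visible. Most outputs are split by part, 8.2.5 treats visit numbers as specific to part and cohort, and the opening of Section 8 promises efficacy summaries for each dose cohort. The gaps in 9.3 and 9.7 could be loose wording to be settled in table shells. This does not fully answer the point. A summary for each dose cohort does not say how placebo is pooled. And because 9.3 and 9.7 name the part for some outputs and not for others, it is unsafe to assume an implied split.

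The second defence is that the schedule of assessments sits in the protocol, so no mixing is demonstrated. That stands. The SAP's statement that laboratory tests are obtained at each study visit supports the laboratory case, except for coagulation, which is done at Screening only (9.3.4). The spirometry visits are not stated. If only one cohort is assessed at Visit 6, nothing is mixed there. If EOS has its own label, as the SAP's repeated use of an EOS visit name suggests it might, the SAD element disappears.

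Third, pooling is a deliberate response to one planned placebo subject in each of Cohorts 1, 2 and 3. That is a fair reason to pool, but not to pool across unlike times.

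Two stronger readings are tempting. A reader might infer that the adverse event and vital sign tables also mix parts. Sections 9.2 and 9.4 call for output by part, and pooling within part is their natural reading, even though 6.1 does not say so. A reader might also infer that a treatment comparison is biased by a known amount. The SAP plans no test of these data, and the shares above are planned head-counts, not estimates of bias.

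**Conclusion.** The wording gap is real and minor. Following 6.1 and 6.4 as written, the placebo rows in the descriptive laboratory tables, the spirometry descriptive and PCS tables and the FEV1 change summary can combine different times relative to dosing, wherever the assessment is done at that visit in more than one cohort. The Visit 6 shares illustrate this; they depend on the unseen schedule, on planned numbers without Amendment 5 and, for Cohort 4, on an inferred visit layout.

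The consequence is limited. All outputs are descriptive and no error rate is affected. The listings keep placebo by cohort, the by-subject plots are split by part, and 6.1 notes that after early closure not every output may be needed. The contradiction in the 8.2.5 visit range is a separate slip that rests on no assumption; it concerns the symptom diary and adds no weight to the pooling point.

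**What to change.** - In 6.1, pool placebo within study part (SAD placebo, MAD placebo) and assign Amendment 5 placebo subjects to their own part.
- In 9.3, 9.7 and 9.7.1, add the split by study part to the descriptive laboratory tables, the spirometry descriptive and PCS tables, and the FEV1 change summary.
- Within MAD, summarize by-visit placebo data by time relative to dosing (dosing day, about 24 hours after the last dose, follow-up, EOS) instead of by visit number.
- In 8.2.5, correct the MAD visit range to agree with the Cohort 3 list (to Visit 9) and the Cohort 4 list (to Visit 14).

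The work is SAP wording and table shells. The price is smaller placebo columns: planned 2 for SAD and 6 for MAD, plus Amendment 5 subjects. At dosing times that only one cohort reaches, n is smaller still; on dosing days 6 to 10 only the 5 planned Cohort 4 placebo subjects contribute. Showing placebo by cohort would also remove the mixing, but it would leave Cohort 3 placebo at n = 1, with no SD, so alignment by time relative to dosing is the better choice.
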